### 7.4. CLASSIFICATION OF RESPONDER STATUS

#### 7.4.1. Classification as a responder

To be a 600 mg responder, a subject must meet both of the following conditions:

- 1) Must have attained a maximum tolerated single dose (MTD) ≥600 mg of peanut protein on Exit DBPCFC
- 2) Must not have experienced more than mild symptoms through 600 mg of peanut protein on Exit DBPCFC.

Classification as a 300 mg responder and a 1000 mg responder are defined similarly.

#### 7.4.2. Classification as a non-responder

If a subject cannot be classified as a responder, then that subject should be classified as a non-responder. If a subject meets any of the following conditions, then the subject is a non-responder:

- 1) Discontinued before the Exit DBPCFC or did not undergo an Exit DBPCFC for any other reason
- 2) Failed the Exit DBPCFC (e.g., a subject who did not tolerate a single dose of at least 600 mg of peanut protein with at most mild symptoms is a 600 mg non-responder).

Classification as a 300 mg non-responder and a 1000 mg non-responder are defined similarly.

#### 7.4.3. Exit DBPCFC imputation rules for non-responders

As a general rule, subjects who do not undergo an Exit DBPCFC for any reason will be categorized as desensitization non-responders and their MTD at the Exit DBPCFC will be imputed using their MTD at the Screening DBPCFC.

#### 7.4.4. Classification of Escalation and OIT Maintenance Failures

Non-responders who did not undergo the Exit DBPCFC are broadly categorized as either escalation failures or OIT maintenance failures. An escalation failure is a subject who is unable to achieve at least one at-home dose of 300 mg/d of peanut protein by 40 weeks (Protocol Section 3.2), discontinuing dosing prematurely either during the Initial Escalation period or during the Up-dosing period.

Subjects unable to tolerate a daily maintenance of 300 mg of study product for at least the last 2 weeks of dosing prior to Exit DBPCFC, free of any symptomatic therapy that was initiated during the course of OIT, will be considered OIT maintenance failures.

The 3 non-responder subcategories are summarized in Table 7.1.

Table 7.1 Non-Responder Subcategories for Subjects Who Do Not Undergo the Exit DBPCFC

Non-Responder Subcategory	Study Period Last Dose Was Taken	Definition of Period
Escalation Failure	Initial escalation	The last dose of study drug was taken during Initial Escalation Visit Day 1 or Day 2. No at-home doses were taken.
Escalation Failure	Up-dosing	The last dose of study drug was taken after Initial Escalation Visit Day 1 or Day 2 and before the first at-home dose of 300 mg.
OIT Maintenance Failure	Maintenance	At least one at-home dose of 300 mg was taken.

Classification of the primary reason a subject discontinued before the Exit DBPCFC provides a further sub-classification of non-responder subcategories, and will be determined during blinded data review prior to database lock and overall study unblinding.

The primary reason for discontinuation will be classified into one of the following categories:

- Discontinued due to reason related to treatment, including: escalation failure, OIT maintenance failure, treatment-related AE causing permanent discontinuation of study drug, or death
- Discontinued due to reason unrelated to treatment

#### 7.5. DATA DERIVATIONS AND DEFINITIONS

The following definitions and derivations will be used throughout this study:

• Study Day is calculated as (assessment date – first dose date + 1) for assessments and visits performed on or after the first dose date, and (assessment date – first dose date) for assessments and visits prior to the first dose date.

- Baseline is defined as the last non-missing value prior to the first dose of randomized study treatment.
- Change from baseline is calculated as observed value after the first dose baseline value.
- Screening period is defined as the time period beginning with the date and time of informed consent through the first dose of randomized study drug excluding the screening DBPCFC period. The last day of the screening period is the day before the first dose of randomized study treatment. Additional details on handling a DBPCFC given on non-consecutive days is provided below.
- Screening DBPCFC Period is the period of time starting with the first dose of DBPCFC product up through the first of:
  - 1. 24 hours after the last dose of DBPCFC product or
  - 2. first dose of randomized study drug
- Initial Escalation period is defined as the time period beginning with the date and time of the first dose of randomized study product in clinic and ending with the date of the last dose of randomized study product taken prior to Up-dosing.
- Up-dosing period is defined as the time period beginning with the date and time of the first home dose of study product at 3 mg, and ending with the date and time of first in-clinic dose at 300 mg. This period will be, ideally, 20 weeks in duration, but may be extended to a maximum of 40 weeks to accommodate dose reductions and re-escalations, if necessary.
- Maintenance period is defined as the time period beginning with the date and time of the first home dose of study product at 300 mg and ending with the date of the last dose of randomized study product taken prior to Exit DBPCFC. Ideally, this period will be 24 weeks in duration, but it may be extended to accommodate dose reductions and re-escalations by up to an additional 4 weeks (for a maximum Maintenance Period duration of 28 weeks), or to a total Treatment Phase duration of 68 weeks, whichever occurs first. For subjects who continue maintenance dosing after the Exit DBPCFC but prior to the rollover to ARC004, those data will be attributed to the maintenance period.

- Exit DBPCFC period is defined as the time period beginning with the date and time of the first DBPCFC dose after the Maintenance Period and through 24 hours after the last dose of DBPCFC product.
- The DBPCFC is given in 2 parts, either on the same day, on consecutive days, or occasionally on non-consecutive days. For the non-consecutive days, the period of time more than 24 hours after the first part and before the second part begins will be attributed as follows
  - 1. For the Screening DBPCFC this is attributed to the Screening Period
  - 2. For the Exit DBPCFC Period it is attributed to the maintenance period.
- The active treatment period is defined as the time period beginning with the date and time of the first dose of randomized study product and ending with the date and time of the last dose of randomized study product.
- Duration of active treatment period (days) for AR101 and placebo is calculated as the date of last dose minus the date of first dose plus 1, excluding the DBPCFC periods.
- The Exit DBPCFC is defined as indeterminate if the subject was not able to tolerate the placebo challenge up to and including a dose of 1000 mg (2043 mg cumulative).

# 7.6. MISSING DATA

All AEs with partial/missing dates and times will be considered Treatment Emergent Adverse Events (TEAEs) unless a partial date clearly indicates that it occurred prior to first dose of study treatment or more than 30 days after last dose of treatment. All therapies with partial or missing dates and times recorded on the Concomitant Medication or Non-Drug Therapy CRF pages will be considered concomitant unless a partial stop date and time clearly indicates it was stopped prior to the first dose of study treatment. Start and stop dates will be imputed when partial dates are present as needed to determine treatment emergent events and concomitant medications. No imputation will be done for a completely missing start/stop date or for subjects who did not receive study treatment.

Start dates with a missing day but which have month and year populated will be imputed such that:

- If the provided month and year match the month and year for that subject's first dose date, then the Day 1 date will be used
- In all other cases the 1st of the month will be used with the provided month and year

Start dates with a missing day and month but which have year populated will be imputed such that:

- If the provided year matches the year for that subject's first dose date, then the first dose date will be used
- In all other cases the 1st of January will be used with the provided year

Stop dates will be imputed as follows:

- Missing day with a provided year and month will use the last day of the month
- Missing day and month with provided year will use December 31

If the imputed stop date is greater than the last study date for the subject, then the imputed date will be replaced with the last known subject date.

The reported date of the most recent reaction to peanut on the peanut allergy history CRF page and date of diagnosis of peanut allergy will be imputed when the month or day is missing as follows:

- Missing day is set to 1 if the same year and month as the informed consent date. Otherwise it is set to 15
- Missing month and day are set to Jan 1 if the same year as the informed consent date. Otherwise it is set to July 1.

Where the severity score of a symptom is missing during screening or exit DBPCFC, the severity score will be imputed as severe.

For the primary and key secondary endpoints involving desensitization rates, if a subject discontinues prior to the exit DBPCFC, they will be considered non-responders. Other sensitivity analyses involving alternative methods for handling subjects with missing exit DBPCFC are described in section 9.2.

For the key secondary endpoint of maximum severity of symptoms, if a subject discontinues prior to the exit DBPCFC, the maximum severity of symptoms during the exit DBPCFC will be imputed using the maximum severity of symptoms during the screening DBPCFC.

No imputations will be made for other missing data, unless specified otherwise.

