*For explanation of contingent/optional doses indicated in parentheses refer to Section 6.6.2

For each subject, a "blinded" Evaluating Physician (Blinded Assessor) is to be designated to assess the tolerability of the challenge doses presented in the DBPCFC. The Blinded Evaluating Physician is not to be involved directly in the oversight of study product dosing (neither initial escalation, nor up-dosing, nor maintenance), nor the assessment or management of adverse events (for details refer to the Masking Plan). To the extent practicable, the same Blinded Evaluating Physician who determines DLSs in the Screening DBPCFC should determine DLSs in the Exit DBPCFC.

Vital signs (blood pressure and pulse rate) are to be measured just prior to each challenge dose of the DBPCFC or at 15 to 20 minute intervals post-dose, if the between challenge-dosing interval is prolonged. Assessment for signs and symptoms of allergic reaction is to be performed at the time that vital signs are checked.

The DBPCFC is halted when the investigator determines that dose-limiting symptoms have occurred. Dose-limiting symptoms, in the setting of the DBPCFC, are any symptoms that, in the investigator's assessment, indicate poor tolerability of the last challenge dose administered, and preclude safe advancement to the next challenge dose.

Dose-limiting symptoms, typically objective symptoms (signs), indicate a positive reaction and termination of dosing. The criteria for determining if symptoms are dose limiting during DBPCFC are the same as for determining whether a specific dose during up-dosing is tolerated (Section 6.7) with the exception that even mild symptoms, if they require pharmacological treatment, will be considered dose-limiting.

As with up-dosing, severe symptoms will always be assessed as dose limiting; and moderate symptoms, with only rare exceptions (requiring a documented explanation), will also be assessed as dose limiting. Mild symptoms, on the other hand, may or may not be assessed as dose-limiting (Section 6.7).

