Based on experience from Phase 2, most acute allergic responses to dosing that are characterized by mild symptoms would be anticipated to meet the above criteria. If, however, an allergic response to dosing is characterized by mild symptoms that do not meet all of the above criteria (eg, has mild symptoms occurring in 2 or more organ systems, requires treatment with 2 doses of antihistamine or 1 dose epinephrine, shows progression in severity or distribution over time, is protracted in duration, or includes objective wheezing), then even though the allergic symptoms may be mild, the dose should be assessed to be not tolerated. If a dose elicits mild symptoms that do not fit all of the above criteria and the dose is assessed to be tolerated, then a brief explanation as to why the dose was considered tolerated must be recorded in the CRF.

Moderate symptoms: In general, if a dose elicits moderate symptoms, the dose will be assessed as not tolerated. There may, however, be rare occasions when a dose eliciting moderate symptoms could be assessed as tolerated. Generally, this would only be the case for a transient, self-limited (requiring no intervention and resolving completely) symptom occurring in a single organ system. In addition, typically the symptom would be subjective only. Any dose associated with moderate symptoms and assessed as tolerated must be accompanied by a brief explanation in the CRF as to why the dose was considered tolerated.

Severe symptoms: In nearly all cases, if a dose elicits severe symptoms, the dose will be assessed as not tolerated. Whenever a dose elicits an allergic response characterized by 1 or more severe symptoms, the crucial decision, after adequate treatment for the allergic reaction has been administered, will be to determine whether the subject should continue in the study, dosing at a reduced dose level, or be discontinued early from the study.

The determination of tolerability will decide the course of action to be taken in response to doserelated reactions (Section 6.7.3).

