#### 7.3. MAXIMUM TOLERATED DOSE AT DBPCFC

The MTD for a DBPCFC is defined as the maximum single dose of peanut protein resulting in no more than mild symptoms and assessed by the investigator to have been tolerated (i.e., subject did not experience any dose-limiting symptoms). Any symptom requiring treatment is inherently dose-limiting; thus, a dose during a DBPCFC cannot be considered "tolerated" if treatment was deemed necessary by the investigator. The MTD at the Screening DBPCFC will be used as the baseline amount of peanut protein tolerated. If a subject is administered non-standard doses at a DBPCFC, the MTD will be considered as the highest standard dose (whether administered or not) less than the highest tolerated nonstandard dose.

When describing the MTD at the Exit DBPCFC, in terms of the cumulative amount of peanut protein, the 1 mg dose will not be included. Thus subjects who tolerate all dose levels from 3 mg to 300 mg or 1 mg to 300 mg have a cumulative MTD of 443 mg.

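### SAP 7.6 grades every unscored food-challenge symptom as severe, even at a dose recorded as tolerated, which protocol 6.6 rules out; the likely effect is small and the repair cheap

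*SAP*

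**What the plan says.** The imputation rule in SAP 7.6 is one sentence: "Where the severity score of a symptom is missing during screening or exit DBPCFC, the severity score will be imputed as severe". It covers both challenges and every dose.

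On the challenge itself, protocol 6.6 says that "severe symptoms will always be assessed as dose limiting", and that "moderate symptoms, with only rare exceptions (requiring a documented explanation), will also be assessed as dose limiting". The challenge is halted once dose-limiting symptoms have occurred. Mild symptoms may or may not be dose limiting.

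The SAP uses the grade in three places:

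- SAP 7.3 defines the maximum tolerated dose (MTD) as the "maximum single dose of peanut protein resulting in no more than mild symptoms and assessed by the investigator to have been tolerated".
- SAP 7.4.1 asks for an MTD of at least 600 mg and, as a separate second condition: "Must not have experienced more than mild symptoms through 600 mg of peanut protein on Exit DBPCFC". It adds: "Classification as a 300 mg responder and a 1000 mg responder are defined similarly".
- SAP 9.3.2 takes each child's worst grade at any Exit dose, scored 0 to 3. A subject without an Exit challenge is given the worst grade from Screening.

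**The concern.** Under protocol 6.6, a symptom at a dose that was assessed as tolerated cannot have been severe. The SAP rule can therefore create a record, severe but tolerated, that the protocol excludes. Because the second responder condition in SAP 7.4.1 looks at grades separately from tolerability, the imputed grade overrides a pass that the blinded assessor observed.

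The endpoints exposed are both regional primaries, the response-rate key secondaries and the maximum-severity key secondary. The tables can also disagree with each other: the same child can count as a 1000 mg success in the MTD analyses and as a failure in the response-rate table.

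The planned sensitivity analyses do not reach this. The worst-case and tipping-point analyses (SAP 9.2) and the multiple imputation (SAP 9.4) deal with a missing Exit challenge; another analysis leaves out indeterminate challenges. None varies a missing grade inside a completed challenge.

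**Working it through.** **1. The plan's own power figures.** Inputs (protocol 9.4): 495 children, 3:1, so n = 371.25 and 123.75; two-sided 0.05. North America: 50% vs 20%, margin δ = 0.15. Europe: 30% vs 15%, δ = 0. With the Farrington-Manning normal approximation,

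power = Φ{[(p1 − p2 − δ) − 1.96·SE0] / SE1},

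where SE0 uses the rates constrained to the null and SE1 the design rates.

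- North America: constrained rates 0.458 and 0.308, SE0 = 0.0489, SE1 = 0.0443; (0.15 − 1.96 × 0.0489)/0.0443 gives 88.9%. The plan states about 89%.
- Europe: SE0 = 0.0457, SE1 = 0.0399; power 93.5%. The plan states at least 93%.

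Both figures reproduce, and neither is in dispute.

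**2. What one missing grade does.** Take a child who tolerated every Exit dose from 3 to 1000 mg, with no symptom worse than mild, and apply SAP 7.3, 7.4.1, 7.6 and 9.3.2.

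| Dose with the ungraded symptom | 300 mg status | 600 mg status | 1000 mg status | Maximum severity | MTD |
|---|---|---|---|---|---|
| 3 to 300 mg | nonresponder | nonresponder | nonresponder | 3 | 1000 mg |
| 600 mg | responder | nonresponder | nonresponder | 3 | 1000 mg |
| 1000 mg | responder | responder | nonresponder | 3 | 600 mg |

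The MTD column reads SAP 7.3 literally, as the highest single dose that itself meets the definition. If the grade is set to mild instead, the child is a responder at all three levels with maximum severity 1. If it is set to moderate, the child is still a nonresponder at the affected levels, but with severity 2.

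**3. Size, under an assumed rate.** The documents give neither a missing-grade rate nor a symptom count. Assume two symptom records per responder and a share m of grades missing. The share of responders flipped is 1 − (1 − m)²: 1.0% at m = 0.5%, 2.0% at m = 1% and 5.9% at m = 3%. Rounded, this is 2% with a range of 1-6%.

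If the same share f is flipped in both arms, the difference falls by f × (p1 − p2):

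- North America: 0.02 × (50 − 20) = 0.6 points; range 0.01 × 30 = 0.3 to 0.06 × 30 = 1.8.
- Europe: 0.02 × (30 − 15) = 0.3 points; range 0.15 to 0.9.

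Putting p1(1 − f) and p2(1 − f) into the power formula:

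| f | North America | Europe |
|---|---|---|
| 0 | 88.9% | 93.5% |
| 1% | 87.8% | 93.2% |
| 2% | 86.5% | 92.8% |
| 6% | 80.8% | 91.4% |

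**4. How many flips would change the result.** With counts at the design rates and only AR101 responders flipped, the North America test (186/371 vs 25/124, z = 3.06) is lost at 22 flips, 11.8% of 186. The Europe test (111/371 vs 19/124, z = 3.20) is lost at 24, 21.6% of 111.

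**5. Direction for maximum severity.** Imputing severe at a tolerated dose counts against whichever arm has the gap. At the dose that stopped the challenge, the true grade may have been mild or moderate, and 3 is then too high. Where the child is on placebo, that favours AR101. Every randomized subject had dose-limiting symptoms at Screening (protocol 3.1), so an imputed 3 can also be carried forward from there; its direction depends on which arm has more subjects without an Exit challenge.

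**The case against.** The strongest defence is that a worst-case rule for a missing component of the primary endpoint is a respectable choice in a superiority trial, and that missing grades should be rare. Desensitization status is a major query item to be resolved before a subject is unblinded (SAP 2.5 and 11), responder status is settled in blinded review before lock (SAP 11), and data are checked for missing values (SAP 15). This stands as an argument about size. It does not change the rule for grades that stay missing. The worst-case defence also holds only for response rates, where the rule can only remove responders; for maximum severity it can favour AR101.

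A second objection is that tolerated does not mean mild. That is right: protocol 6.6 allows a rare tolerated moderate symptom. The documents support grade 1 or 2 at a tolerated dose, not automatic responder status. Mild follows only where the required explanation is absent.

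A third is that protocol 6.7.2 is softer: "In nearly all cases, if a dose elicits severe symptoms, the dose will be assessed as not tolerated". That sentence concerns study-product doses, and Table 6-2 in the same section lists severe as not tolerated. Section 6.6 governs the challenge.

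A reader might also infer three things that the documents do not support:

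- That any missing grade loses the North America primary. A gap at the 1000 mg dose leaves 600 mg response intact.
- That the treatment difference falls by a full point at a 2% flip. That figure, 0.02 × 50, is the loss in the AR101 arm alone; placebo loses 0.02 × 20 = 0.4, which leaves 0.6.
- That AR101 must lose more because its subjects take more challenge doses. This is plausible, but no symptom counts are given from which to show it.

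**Conclusion.** The conflict between SAP 7.6 and protocol 6.6 is real. For a child who tolerated 1000 mg, one ungraded symptom always costs the Europe primary and sets maximum severity to 3; whether it costs the 600 and 300 mg endpoints depends on the dose at which it falls.

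The expected effect is small: 0.6 points on the North America difference (0.3-1.8) and about 2.4 points of power at a 2% flip, rising to about 8 points at 6%. These sizes rest on an assumed missing-grade rate, two symptom records per responder, every responder having symptoms, and equal shares in both arms. They also rest on reading SAP 7.6 as feeding responder status. The SAP does not say so expressly, but its wording is unrestricted and sections 7.3 and 7.4.1 use the grades.

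This is a correction that should be made, not a threat to the trial's conclusion.

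**What to change.** Amend SAP 7.6 before database lock, while project staff are still blinded, so that the imputed grade agrees with the dose's recorded tolerability:

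- At a dose assessed as tolerated, impute mild, or moderate if the CRF carries the required explanation for a tolerated moderate symptom.
- Impute severe only at the dose recorded as dose limiting.

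Add two sensitivity analyses:

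- (a) The present all-severe rule, for the response and maximum-severity endpoints.
- (b) For maximum severity, ungraded symptoms at the dose-limiting dose imputed as moderate, both at Exit and in Screening values carried forward. Without (b), the new main rule would drop the part that counts against AR101 on response and keep the part that can favour it on severity.

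The data needed already exist: SAP 10.5 says that dose-limiting symptoms are identified in each challenge. The cost is a SAP amendment, one derivation and two added analyses. The main response analysis becomes slightly less conservative, which (a) covers. SAP 1.1 records that Version 2 was written after several subjects had been unblinded, so the amendment should state that those making it had no access to treatment assignments.
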